12.3 Adverse Event Reporting

12.3.1 Notification of Serious Adverse Events

The Sponsor has requirements for expedited reporting of SAEs meeting specific criteria to worldwide regulatory authorities in accordance with ICH guidelines and local regulatory requirements. Therefore, the Investigator must notify the Sponsor immediately regarding any SAE that occurs after informed consent through the final follow-up visit (Days 52–59) via transmission of a Serious Adverse Event Report (SAER) by the study site to the safety vendor by email within 24 hours of awareness that an SAE has occurred, with a copy to the Medical Monitor. Contact details will be provided to all sites. An optional initial report can be made via telephone, but a completed SAER must still be emailed within 24 hours of the site's knowledge of the event.

The investigational site will be provided with SAER forms wherein the following information is requested:

- Subject identification, Investigator name, and site number
- SAE information: event term, onset date, AE severity, and causal relationship
- The outcomes attributable to the event (e.g., death, a life-threatening AE, inpatient hospitalization, prolongation of existing hospitalization, a persistent or significant disability or incapacity, or other important medical event[s])
- A summary of relevant test results, pertinent laboratory data, and any other relevant medical history
- The first and last dates of study drug administration (NOTE: as this is a double-blind study, SAERs should not indicate specific study drug assignments)
- Indicate if the study drug was discontinued or the study drug administration schedule modified

Supplemental information may be requested from the site, including hospital records, laboratory results, radiology reports, progress notes, admission and emergency room notes, holding and observation notes, discharge summaries, autopsy reports, and death certificates.

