12.5 Adverse Event Classification

12.5.1 Relationship to Investigational Drug

The Investigator's assessment of causality must be provided for all AEs (serious and non-serious) (Table 11). An Investigator's causality assessment is the determination of whether there exists a reasonable possibility that the study drug caused or contributed to an AE.

Clinical failure that qualifies as an AE without evidence of study drug toxicity should be considered unrelated to study drug.

These criteria, in addition to good clinical judgment, should be used as a guide for determining the causal assessment. If the event is thought to be unrelated to study drug administration, then an alternative explanation should be provided.

Table 11: Guidelines for Assessing Relationship of Event to Study Drug

Unrelated	There is little or no chance that the Investigational Product caused the AE; other conditions, including concurrent illnesses, progression or expression of the disease state, or a reaction to a concomitant medication best explain the event
Related	The association of the AE with the Investigational Product is unknown; however, the AE is not clearly due to another condition, or a reasonable temporal association exists between the AE and treatment administration and, based on the Investigator's clinical experience, the association of the AE with the Investigational Product seems likely

Abbreviation: AE = adverse event.

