3.7. Missing, Unused, and Spurious Data

The following rules for missing data will be followed:

- For the primary efficacy outcome measure of all-cause mortality for the FDA, subjects with a missing death date on the eCRF will be considered to have died. The subject's vital status will be determined using available sources such as the subject, the subject's contacts, hospital and other medical records and public records.
- For the primary efficacy outcome measure of global response for the EMA, subjects with a missing response are considered an indeterminate response and are included in the denominator for analyses in the mITT population.
- Adverse Event, Death Date and Prior/Concomitant Medication Date Imputations will follow the rules described in [Appendix 7 Adverse Event and Prior/Concomitant Medication Date Imputations](#).
- The CTCAE grade and causality assessment for adverse events should not be missing (except in the case of a death reported only on the Survival Status eCRF which should be considered an adverse event of Death NOS) and will be queried for a value. Should there be missing data for adverse events other than Death NOS, adverse events with missing severity will be considered severe (Grade 3) and adverse events with missing causality will be considered related to study drug. For deaths from the Survival Status eCRF (and not on the Adverse Event eCRF), missing severity will be considered Grade 5 (death) and missing causality will be considered not related to study.
- Unless otherwise specified, missing values for other individual data points will remain as missing. Missing values will not be imputed and only observed values will be used in data analyses and presentation.

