4.5.1. Adverse Events

Verbatim descriptions of AEs will be coded using the latest MedDRA version (version 23.0 or higher). Summary tables will be provided for all treatment-emergent adverse events (TEAEs). A TEAE is defined as an AE that occurs during or after study drug administration and up through the Follow Up visit (Days 52-59). An AE is programmatically defined as treatment emergent if the start date and time is on or after the start date and time of the first dose of study drug. If the time of an AE is missing, it is considered treatment emergent if it starts on the same date as the first dose of study drug. Date Imputations will follow the rules described in [Appendix 8 \(Section 5.8\)](#).

Deaths obtained only through the Survival Status eCRF will not be recorded on the AE eCRF, but will be programmed as an AE with SOC and PT of "Death NOS" and analyzed as an AE/SAE with outcome of fatal.

An overall summary of AEs and TEAEs will include the number and percentage of subjects in each treatment group who experienced at least 1 AE/TEAE in the following categories: any AE, any TEAE, any TEAE up through Day 7, any study drug-related TEAE, any grade 4/5 TEAE, any serious AE (SAE), any study drug-related SAE, any SAE leading to death (that includes SAE started during study with an outcome of death that occurred after the Follow-up Visit), any study drug-related SAE leading to death, any TEAE resulting in interruption of administration of study drug, any TEAE leading to discontinuation of study drug, and any TEAE resulting in study discontinuation. The overall summary of AEs will be repeated for the high risk subgroups defined in [Table 4-1](#).

Subjects with multiple events will be counted only once within each category. CTCAE grade (version 5.0) and relationship will be counted using the maximum grade and the strongest relationship respectively for a subject with multiple TEAEs.

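### Missing causality counts as not related for deaths known only from the Survival Status eCRF, the reverse of the rule for other AEs, so unassessed deaths cannot enter the drug-related fatal SAE count

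*SAP*

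**What the plan says.** SAP 3.7 handles missing causality in a single bullet with two defaults.

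- **AEs in general.** The rule opens "Should there be missing data for adverse events other than Death NOS" and says that "adverse events with missing causality will be considered related to study drug".
- **Deaths on the Survival Status eCRF and not on the AE eCRF.** Here "missing severity will be considered Grade 5 (death) and missing causality will be considered not related to study".

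The same bullet says that grade and causality should not be missing and will be queried, but makes an exception: "except in the case of a death reported only on the Survival Status eCRF which should be considered an adverse event of Death NOS".

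SAP 4.5.1 adds that "Deaths obtained only through the Survival Status eCRF will not be recorded on the AE eCRF". They are instead programmed with SOC and PT of Death NOS and "analyzed as an AE/SAE with outcome of fatal". The overall AE summary in that section has one line for SAEs leading to death and another for drug-related SAEs leading to death. Drug-related SAEs are also tabulated by SOC and PT.

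On the protocol side:

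- Section 12.2 has the Investigator record causal relationship on the eCRF for all AEs and SAEs.
- Section 12.3.1 says that "the Investigator must notify the Sponsor immediately regarding any SAE that occurs after informed consent through the final follow-up visit".
- Section 12.4.1 requires even an event of the disease under study to be entered as an AE if it meets the SAE definition.
- Section 12.5.1 requires an Investigator causality assessment for serious and non-serious AEs alike.

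**The concern.** The gravest outcome gets the less cautious default. Where nobody has judged causality, the SAP assumes a drug relationship for a minor AE and assumes none for a death, and it neither explains the difference nor plans to test it.

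What is at stake is a small set of reported safety counts: drug-related SAEs and, above all, drug-related SAEs leading to death. Someone reading a zero on the second line would take it that the fatal events were assessed and none was attributed to study drug. Under this rule, a zero could also include deaths that were never assessed.

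**Working it through.** The plan states no number of Survival-Status-only deaths, so there is no figure to reproduce. The check is a reading of the rules, followed by an illustration of scale.

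**Step 1: can causality be present for these deaths?** SAP 3.7 imputes only where causality is missing, so a recorded assessment would stand. But causality is recorded with the AE (Protocol 12.2), and SAP 4.5.1 says that these deaths have no AE eCRF record. The exception in SAP 3.7 removes the expectation that causality be present. Whether it also removes the query is unclear from the sentence, but nothing in the SAP asks for one. In practice the default will apply to essentially all of these deaths.

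**Step 2: which outputs change?**

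| Output (SAP 4.5.1) | Does an unassessed Death NOS count? |
|---|---|
| SAEs leading to death; fatal SAEs by SOC and PT | Yes |
| Grade 4/5 TEAEs (if treatment-emergent) | Yes, as Grade 5 |
| TEAEs by SOC, PT and relationship (if treatment-emergent) | Yes, as unrelated |
| Drug-related SAEs, overall and by SOC and PT | No |
| Drug-related SAEs leading to death | No |

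A subject with another SAE judged related would still count once on the overall drug-related SAE line, but the death itself adds nothing.

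**Step 3: the two defaults compared.** Let r be the deaths in an arm assessed as related and u the deaths left unassessed.

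- Drug-related fatal count under the SAP rule for these deaths: r, whatever u is.
- Count under the SAP's general missing-equals-related rule: r + u.

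**Step 4: scale, for illustration only.** Inputs from SAP 3.1 are about 218 randomised at 1:1 and a planned Day 30 mortality of 20%.

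- Subjects per arm: 218 / 2 = 109.
- Expected deaths per arm by Day 30: 109 × 0.20 = 21.8, about 22.
- The share known only from the survival form is not in the documents. At an assumed 5%, 10% and 20%: 21.8 × 0.05 = 1.1; 21.8 × 0.10 = 2.2; 21.8 × 0.20 = 4.4. That is about 1, 2 and 4 deaths per arm.

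| u | r | SAP rule for these deaths | General rule, r + u |
|---|---|---|---|
| 1 | 0 | 0/109 (0%) | 1/109 (0.9%) |
| 2 | 0 | 0/109 (0%) | 2/109 (1.8%) |
| 4 | 0 | 0/109 (0%) | 4/109 (3.7%) |
| 4 | 1 | 1/109 (0.9%) | 5/109 (4.6%) |

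The 20% is an mITT planning rate applied here to all randomised subjects. Using the planned 92 mITT subjects per arm instead gives 92 × 0.20 = 18.4 deaths, and 0.9, 1.8 and 3.7 unassessed at the same shares.

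**The case against.** The other side has real points.

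- **The protocol gives the default some support.** Section 12.5.1 says that clinical failure qualifying as an AE, without evidence of drug toxicity, should be considered unrelated, and Protocol Table 9 makes death from any cause a clinical failure. So the protocol does not point one way only. But that sentence guides a judgement on an event someone has assessed; it does not supply one where nobody has looked.
- **Table 11 does not settle the matter.** A reader might infer that it requires these deaths to be classed as related, since its Related row includes: "The association of the AE with the Investigational Product is unknown; however, the AE is not clearly due to another condition". The row goes on to temporal association and the Investigator's clinical experience, and the table is offered as guidance alongside clinical judgement. It is not an imputation rule for unassessed records. This point stands.
- **The deaths are not hidden.** They carry their own term and appear in the fatal-SAE and relationship tables and in the SAE listing, so a careful reader could largely reconstruct the alternative count. This also stands, though the headline drug-related lines would carry no sign that it is needed.
- **There may be few of them.** SAE reporting runs through Follow-up, and the SAP rule is a fallback for what slips through, such as deaths learned from contacts or public records. The documents neither confirm nor exclude a small number.
- **Missing-equals-related has the opposite fault.** It would report unassessed deaths as drug-related fatalities. That is a fair reason not to make it the only presentation.

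**Conclusion.** The inconsistency is real and limited. SAP 3.7 reverses its own missing-causality rule for one class of deaths without giving a reason, and SAP 4.5.1 keeps those deaths off the form on which the protocol expects them to be recorded and assessed. As a result, an unassessed Survival-Status-only death adds 0 to the drug-related SAE and drug-related fatal SAE counts, where the general rule would add 1. The 1 to 4 deaths per arm shown above rest entirely on an assumed 5% to 20% share.

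Three stronger readings are tempting but unsupported:

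- **That the primary results are affected.** All-cause mortality counts deaths whatever the cause, and global cure makes no use of causality for a death.
- **That the rule favours one arm.** It applies identically to both, and nothing in the documents points to a between-arm effect.
- **That the drug-related fatal count is biased downwards.** This would require some of these deaths to be truly drug-related, which the documents cannot show. They support only that the count ignores unassessed deaths.

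It is worth correcting because it changes a reported safety count and the correction is cheap.

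**What to change.** 1. **SAP 4.5.1.** Replace the statement that these deaths stay off the AE eCRF. Before database lock, query each such death occurring through Follow-up for an AE/SAE record and the Investigator's causality assessment, in line with Protocol 12.3.1, 12.4.1 and 12.5.1.
2. **SAP 3.7.** Remove the not-related default, and state plainly that the causality query covers these deaths.
3. **Tables.** Where causality is still missing after the query, show the death in its own row, labelled *Death NOS, causality not assessed*. Report the drug-related SAE and drug-related fatal SAE counts twice: with these deaths, which matches the SAP's rule for other AEs, and without them.

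The cost is some SAP wording, a few queries and one extra table row. The drug-related fatal count may look slightly less favourable when the unassessed deaths are included.

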3.8. Visit Windows

Study procedures should be completed within the windows provided in the Schedule of Assessments and Procedures in [Appendix 2](#). Summaries of efficacy will be based on the nominal visits. Refer to Section 4.3 for the details.

Summaries of safety outcomes will be provided by Study Day based on the visit windows as specified in the protocol. The safety measurements taken outside the protocol specified visit windows will be considered as unscheduled visit measurements and will not be included in by-visit summaries but will be included in overall worst post-baseline summaries. If more than 1 measurement is available within the visit window, the following rules will be used:

- If there are measurements from both scheduled and unscheduled visits, the measurement taken on the scheduled visit will be used.
- If no scheduled visit is available, the earliest measurement in the window will be used.

Summaries of PK concentrations will be provided by nominal time points. For the “10 minutes prior to end of infusion” time point, this time point will be summarized if it is within -30 minutes prior to end of infusion and 10 minutes after end of infusion. No other time point windows will apply.

3.9. Interim Analyses

No interim analysis except for the safety data review by DSMB as stated below is planned.

3.9.1. Data and Safety Monitoring Board

An independent external DSMB will be established to review safety data. The DSMB will review safety data once when approximately 50% of subjects are randomized and as required for AEs of special interest while the study is ongoing as provided in the DSMB Charter. The DSMB will be comprised of clinicians and a statistician who are experienced in studies of fungal infections. A detailed charter will be developed, compliant with guidelines of the FDA and ICH that describes the roles and responsibilities of the DSMB, the timing of the meetings, as well as the data to be provided for review.

4. STATISTICAL ANALYSIS

4.1. Study Population

4.1.1. Analysis Populations and Subject Disposition

Each subject providing informed consent in the study will be accounted for. The number and percentage of subjects in each of the analysis populations will be summarized overall and by treatment group. The number and percentage of subjects prematurely withdrawing from the study and the primary reason for premature withdrawal (including withdrawal due to COVID-19) will be summarized overall and by treatment group for the ITT and mITT populations as will the number and percentage of subjects prematurely discontinuing treatment regimen and the primary reason for premature discontinuation (including withdrawal due to COVID-19). A separate listing will be provided for those subjects who sign informed consent but are not randomized (screen failures), including their specific reason for exclusion. The number and percentage of randomized subjects identified as failing to meet at least 1 inclusion criterion or meeting at least 1 exclusion criterion, and the specific inclusion criterion not met/exclusion criterion met, will be summarized by treatment group and overall, for the ITT population. A supportive by-subject listing will be generated for all inclusion criteria not met and exclusion criteria met.

Number of subjects in the mITT, and Safety populations will be summarized. A supportive by-subject listing will be generated for all randomized subjects indicating all analysis population assignments and any reason for exclusion from analysis populations (wherever applicable). Inclusions and exclusions from analysis populations will be finalized prior to Database lock and unblinding.

4.1.2. Protocol Deviations

The number and percentage of subjects with at least one, at least one minor and at least one major protocol deviation will be presented by treatment group and overall for the ITT population. The number and percentage of subjects with at least one major protocol deviation by type of deviation will be presented by treatment group and overall. A by-subject listing of all protocol deviations in the ITT population, with a flag for minor and major deviations by treatment group will be produced. All missed visits due to COVID-19 will be noted as protocol deviations and presented in the listing.

4.1.3. Demographics and Baseline Characteristics

Demographic and baseline characteristics information including:

- sex, race, ethnicity, age at time of informed consent, female of child-bearing potential, age category (<65 year, ≥65 years)
- diagnosis at randomization (candidemia only, IC) and final diagnosis (candidemia only vs IC)
- Modified APACHE II score (≥20, <20, and within <20: 10-19, <10)
- diagnostic methodology used ≤96 hours before randomization (for positive *Candida* from blood culture, rapid IVD, gram stain positive for yeast from a specimen obtained from a normally sterile site, and culture specimen obtained from a normally sterile site)
- absolute neutrophil count at Baseline (<500/μL, ≥500/μL)
- absolute neutrophil count, modified APACHE II score and diagnosis at randomization (candidemia only, APACHE II ≥20 or ANC <500/μL; candidemia only, APACHE II score <20 and ANC ≥500/μL; IC, APACHE II ≥20 or ANC <500/μL; and IC, APACHE II score <20 and ANC ≥500/μL)
- height, weight, body mass index (BMI)
- estimated creatinine clearance (eCrCl, based on Cockcroft-Gault formula)
- Child-Pugh score category (<7, 7-9, and no history of liver disease)
- Geographic region (United States, Europe/Israel/Turkey, Asia-Pacific (excluding China/Taiwan), China/Taiwan, South America)

will be summarized by treatment group and overall in the ITT and mITT populations.

BMI (kg/m²), calculated by dividing weight (kg) by height (m²) will be captured in the eCRF.

The Cockcroft-Gault formula for eCrCl is:

$$eCrCl = \frac{[140 - \text{Age (years)}] \times [\text{AIBW (kg)}] \times [0.85 \text{ if Female}]}{72 \times [\text{Serum Creatinine (mg/dL)}]}$$

where AIBW (adjusted ideal body weight) = ideal weight + [0.4 x (actual weight (kg) – ideal weight)]; ideal weight = [height (cm) – 152.4] x 0.9 + 45.5 + 4.5 (if male)

4.1.4. **Medical and Surgical History**

Medical and surgical history, including procedures recorded at screening and subjects diagnosed with COVID-19 at screening will be summarized by treatment group, system organ class (SOC), and preferred term (PT) using the latest version of MedDRA in the Safety and mITT populations. For this summary, subjects with more than 1 medical/surgical history within the same SOC or PT will be counted only once for that SOC or PT.

4.1.5. **Candida Risk Factors**

The number and percentage of subjects with each of the following risk factors at Screening will be summarized by treatment group in the ITT and mITT populations.

Risk factors for candidemia and IC include (but are not limited to):

- Central venous catheter
- PICC (Peripherally Inserted Central Catheter)
- Active malignancy
- Broad-spectrum antibiotic therapy
- Diabetes mellitus
- Immunosuppression
- Major surgery
- Total parenteral nutrition
- Transplant recipient
- Trauma
- End stage renal disease/ dialysis
- Burns

- Pancreatitis
- Other

For subjects who had a catheter and positive blood culture at Screening, a summary of the number and percentage of subjects by type of catheter will be provided. Descriptive statistics for the durations of catheter placement (any catheter and by type of catheter) since the catheter placement and since diagnosis (the first positive blood culture) will also be provided. The durations are defined as the number of days since the catheter placement or the number of hours since the first positive blood culture (if catheter was already in place prior to the first positive blood culture) to the catheter removal date and time. The catheters that were removed prior to the first positive blood culture are not included in the summary. If there is more than one catheter placed across multiple locations, the one with the longest duration is summarized. The number and percent of subjects who had their catheter removed within 48 hours after diagnosis with candidemia and subjects who did not have their catheter withdrawn will be summarized by treatment group in the mITT population. This analysis will be repeated for the subjects diagnosed with candidemia only in the mITT population.

4.1.6. **Systemic Signs of Candidemia and/or IC**

The number and percentage of subjects with each systemic sign at Screening determined to be attributed to candidemia and/or IC by the PI will be summarized by treatment group for subjects in the ITT and mITT populations. Signs include fever, hypothermia, hypotension, tachycardia, tachypnea, and local signs of inflammation. Symptoms include fatigue, pain and myalgia. If there are multiple assessments during Screening, the worst value for each sign or symptom will be used. A by-subject listing of systemic signs and symptoms assessed at Screening, Day 5, Day 14 (± 1), Day 30 (-2), and the Follow-up visit, including the other clinical signs and symptoms reported on the eCRFs, and the PI determination of whether or not the sign/symptom is attributable to candidemia will also be provided.

4.1.7. **Baseline Candida Pathogens**

The number and percentage of subjects with blood or normally sterile tissue/fluid samples collected for culture ≤ 96 hours before randomization will be summarized by treatment group in the ITT population. The draw location and the result (growth of *Candida* or no growth of *Candida*, mutually exclusive) and timing of the most recent positive culture prior to randomization will be summarized by treatment group in the ITT population. The genus and species of *Candida* pathogens identified from baseline blood and sterile site cultures (all unique *Candida* species from the cultures collected within 96 hours before randomization or prior to the first dose of study drug after randomization) will be summarized by treatment group for subjects in the mITT population.

The number and percentage of subjects with the rapid diagnostic test performed will be summarized by treatment group in the ITT population, as well as the type of test, the results (positive or negative) and the *Candida* species.

For each baseline *Candida* species (defined as all unique *Candida* species from the cultures collected within 96 hours before randomization or prior to the first dose of study drug after randomization), a summary of the distribution of minimum inhibitory concentration (MIC) results from the central lab (or if not available, from the local lab) will be presented both by treatment group and for treatment groups combined for subjects in the mITT population in separate tables for each of Rezafungin for Injection, caspofungin, anidulafungin, micafungin, and fluconazole. In addition, for each baseline *Candida* species, the MIC₅₀, MIC₉₀, and MIC_{Range} for Rezafungin for Injection, caspofungin, fluconazole, anidulafungin, and micafungin will be summarized (MIC₅₀ and MIC₉₀ are presented only where there are at least 10 of a particular *Candida* species with susceptibility data available from the central mycology laboratory in each treatment group), will be summarized both by treatment group and for treatment groups combined for subjects in the mITT population. If there is more than 1 isolate of the same *Candida* species prior to first dose, the isolate that has the highest MIC to study drug received (i.e., the highest MIC to rezafungin for Rezafungin for Injection group, the highest MIC to caspofungin for Caspofungin group) is considered the baseline isolate.

A by-subject listing will be provided displaying all MIC results for any baseline *Candida* species that is resistant to echinocandins; a separate by-subject listing will be provided displaying all MIC and disk diffusion zone diameter results for any baseline *Candida* species that is resistant to fluconazole.

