APPENDIX 2: CREATININE CLEARANCE

In the event the local laboratory does not calculate creatinine clearance based on the most recent serum creatinine value, estimate the patient's creatinine clearance using the serum creatinine value provided by the local laboratory, actual body weight, and the appropriate Cockcroft-Gault formula. If necessary, convert serum creatinine values from $\mu\text{mol/L}$ to mg/dL by dividing by 88.4. For example, 100 $\mu\text{mol/L}$ divided by 88.4 equals 1.131 mg/dL :

Males:

$$\text{Creatinine clearance} = \frac{(140 - [\textit{insert age in years}]) \times [\textit{insert weight in kg}]}{72 \times [\textit{insert serum creatinine in mg/dL}]}$$

Females:

$$\text{Creatinine clearance} = 0.85 \times \frac{(140 - [\textit{insert age in years}]) \times [\textit{insert weight in kg}]}{72 \times [\textit{insert serum creatinine in mg/dL}]}$$

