APPENDIX 3: LABORATORY TESTS

Hematology	Serum Chemistry
hemoglobin	blood urea nitrogen ^c
hematocrit	bilirubin (total and direct)
total and differential leukocyte count	alkaline phosphatase
red blood cell count	aspartate aminotransferase
platelet count	alanine aminotransferase
Urinalysis	albumin
pH	sodium
specific gravity	potassium
protein ^a	chloride
glucose	glucose
ketones	creatinine ^b
bilirubin	total protein
blood ^a	calcium (total)
nitrite ^a	bicarbonate ^d
urobilinogen	magnesium
leukocyte esterase ^a	
Coagulation Tests	Additional Tests
PT/INR	serum pregnancy (for females only)
	blood culture within 12 hours of randomization (required for candidemia subjects)

Abbreviations: PT/INR = Prothrombin Time or International Normalized Ratio

- a. If urinalysis is positive for protein, blood, nitrite and/or leukocyte esterase, a microscopic examination (for red blood cells, white blood cells, bacteria, casts, and epithelial cells) will be performed.
- b. At Screening, creatinine clearance will be calculated using the Cockcroft-Gault formula ([Appendix 2](#)).
- c. Study sites that do not perform BUN testing may use a Urea test result, instead, for entry into EDC. If the Urea test result is reported in mg/dL, site staff will need to convert the Urea test result(s) for their subject(s) to a corresponding BUN value by using the following conversion factor:
 - $\text{Urea [mg/dL]} \times 0.467 = \text{BUN [mg/dL]}$
 If the Urea test result is reported in mmol/L, site staff will not need to convert this, as $\text{Urea [mmol/L]} = \text{BUN [mmol/L]}$. In this circumstance, the Urea (mmol/L) value can be entered directly into the eCRF as BUN (mmol/L). File a copy of this memo in the On-Site Study File.
- d. Total CO₂ may be used instead of bicarbonate as they are interchangeable and no conversion is required.

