6. CHANGES TO PLANNED ANALYSES

There are no changes between the protocol-defined statistical analyses and those presented in this SAP.

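### The SAP's baseline creatinine clearance uses adjusted ideal body weight for every subject, which inflates the value below ideal weight and differs from the protocol's actual-weight formula for the same Screening quantity

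*SAP*

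**What the plan says.** SAP Section 4.1.3 lists among the baseline characteristics "estimated creatinine clearance (eCrCl, based on Cockcroft-Gault formula"), summarised by treatment group and overall in the ITT and mITT populations. Its weight term is the adjusted ideal body weight, "where AIBW (adjusted ideal body weight) = ideal weight + [0.4 x (actual weight (kg) – ideal weight"), with "ideal weight = [height (cm) – 152.4] x 0.9 + 45.5 + 4.5 (if male"). The definition carries no condition on whether actual weight lies above or below ideal weight.

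Protocol Appendix 2 tells sites to "estimate the patient's creatinine clearance using the serum creatinine value provided by the local laboratory, actual body weight, and the appropriate Cockcroft-Gault formula". That instruction opens as a fallback: "In the event the local laboratory does not calculate creatinine clearance based on the most recent serum creatinine value". Note b to the laboratory table in Protocol Appendix 3 carries no such condition: "At Screening, creatinine clearance will be calculated using the Cockcroft-Gault formula", with a pointer to Appendix 2.

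The SAP's version history (Appendix 9) records that V4.0 moved the clearance formula to adjusted ideal body weight. It gives no reason and does not mention Appendix 2.

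**The concern.** Two things look wrong. First, the adjustment has no lower branch. Adding 40% of the difference from ideal weight tempers the weight of a heavy subject. In a light subject the difference is negative, so the same expression removes only 40% of the deficit and leaves a weight higher than the one measured. Second, the SAP and the protocol give different formulas for the same Screening value.

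At stake is the accuracy of one reported description of the population. Renal function would be overstated in every subject below ideal weight, not only in the clinically underweight, and the reported values would not match what Appendix 2 produces. Both documents foresee subjects at the extremes of weight: the notes to the dosing schedule ask for attention to subjects under 50 kg and over 85 kg.

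**Working it through.** **Inputs from the documents.** The SAP formula and its ideal weight come from Section 4.1.3, and the protocol formula from Appendix 2. Age, the factor 0.85 for women, the divisor 72 and serum creatinine enter both in the same way; only the weight differs. Neither document prints a clearance result to reproduce. The one worked figure in Appendix 2, the unit conversion, does reproduce: 100 / 88.4 = 1.131 mg/dL.

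**Algebra.** Write I for ideal weight, W for actual weight and A for the SAP's adjusted weight.

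- A = I + 0.4 × (W − I)
- A − W = 0.6 × (I − W), which is positive whenever W < I
- SAP clearance / Appendix 2 clearance = A / W, because all other terms cancel

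The direction of the error below ideal weight therefore follows from the formula alone, and the two formulas agree only at W = I.

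**Numbers.** The documents give no height or weight distribution, so the subjects below are assumptions chosen to show the range.

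- Man, 175 cm: I = (175 − 152.4) × 0.9 + 45.5 + 4.5 = 70.34 kg. At 50 kg, A = 70.34 + 0.4 × (50 − 70.34) = 62.2 kg, and 62.2 / 50 = 1.244.
- Woman, 162 cm: I = (162 − 152.4) × 0.9 + 45.5 = 54.14 kg. At 45 kg, A = 54.14 + 0.4 × (45 − 54.14) = 50.5 kg, and 50.5 / 45 = 1.122.

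The clearance columns further assume age 65 and creatinine 1.0 mg/dL. The percentage column does not depend on either.

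| Subject | Actual kg | SAP kg | SAP vs Appendix 2 | Appendix 2, mL/min | SAP, mL/min |
|---|---|---|---|---|---|
| Man 175 cm | 45 | 60.2 | +34% | 46.9 | 62.7 |
| Man 175 cm | 50 | 62.2 | +24% | 52.1 | 64.8 |
| Man 175 cm | 60 | 66.2 | +10% | 62.5 | 69.0 |
| Man 175 cm | 100 | 82.2 | −18% | 104.2 | 85.6 |
| Woman 162 cm | 40 | 48.5 | +21% | 35.4 | 42.9 |
| Woman 162 cm | 45 | 50.5 | +12% | 39.8 | 44.7 |
| Woman 162 cm | 100 | 72.5 | −28% | 88.5 | 64.2 |

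**Where the value is used.** In the SAP it appears only in the baseline table of Section 4.1.3. It is not a stratification factor (Section 1.2.1), does not define a population (2.6), and is not among the efficacy subgroups (2.8, 4.3.3) or the higher-risk safety subgroups (Table 4-1). The nephrotoxicity definition in Section 4.5.2 uses serum creatinine.

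**The case against.** The strongest reply is that this is a descriptive row, that the choice of weight in Cockcroft-Gault is the analyst's, and that the change was logged openly in V4.0. Appendix 2 is also worded as a fallback for laboratories that do not calculate clearance themselves. Much of this stands. The row feeds no inference, and the edit was deliberate and disclosed. The fallback wording weakens the conflict only in part, because Appendix 3 note b sends the Screening value to Appendix 2 without that condition. An analyst's choice of weight may explain an adjustment for heavy subjects. It does not explain crediting light subjects with weight they do not have.

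A reader might infer more than the documents support:

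- **Misplacement around 50 mL/min.** Some assumed subjects do fall on opposite sides of that value (46.9 against 62.7 for the 45 kg man). But Section 4.1.3 sets cuts for age, APACHE II, neutrophil count and Child-Pugh score and none for clearance. The protocol's cut belongs to oral fluconazole step-down, from Day 4 at the earliest, and Appendix 2 refers to the most recent creatinine. A Screening table need not match that class under any weight formula.
- **Biased comparison between arms.** The same formula applies to both randomised groups, and nothing in the documents points to a differential effect.
- **Many subjects affected.** The documents caution about low weight but give no frequency.
- **A false statement in SAP Section 6.** That section says "There are no changes between the protocol-defined statistical analyses and those presented in this SAP". Protocol Section 13.2 lists the characteristics to be summarised and does not name creatinine clearance, so there is no protocol-defined analysis of it for Section 6 to contradict.

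**Conclusion.** The point holds as a minor error in a reported value. The SAP formula overstates baseline clearance relative to measured weight for every subject below ideal weight, by a factor A / W. In the assumed examples the inflation runs from 10% (man of 175 cm at 60 kg) to 34% (same height, 45 kg). Above ideal weight the SAP value is lower than the Appendix 2 value, by 18% and 28% in the two examples at 100 kg. The direction rests only on the formula; the sizes rest on assumed heights and weights. How far the table's mean or median would move cannot be judged, because no weight distribution is given. No primary or secondary conclusion depends on this row.

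**What to change.** In SAP Section 4.1.3, compute the baseline row with the Appendix 2 formula and actual body weight, so that the SAP and Protocol Appendices 2 and 3 describe one quantity. If the team wants to keep an adjusted weight, the minimum is to apply it only when actual weight exceeds ideal weight, to use actual weight otherwise, and to label the row as different from Appendix 2. A sentence giving the reason for the adjustment should go with it.

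The cost is one formula line and a footnote. Height and weight are already collected at Screening, and no other analysis has to be rerun.
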